- The Efficacy Analysis Set will be a subset of the Safety population with measurable AML disease at baseline and at least one post-baseline disease response assessment. Subjects in this set will be used for all efficacy summary tables.
- Pharmacokinetic Analysis Set will be a subset of the Safety population with at least 1 quantifiable plasma concentration collected post-dose without important protocol deviations/violations or events thought to significantly affect the PK. Summary tables for PK concentrations and parameters will be based on this set of subjects.

F. Data Display Characteristics

Data displays produced for this study will include three types—data listings, summary tables, and figures.

Unless stated otherwise, data listings will be produced for all recorded data. Data listings will simply list the data recorded on the CRF or derived for each subject. They will be ordered by treatment, subject number, and date and time of assessment, where applicable. When expedient, additional levels of ordering hierarchy may reflect subsets of assessments within subject. Additional listings may be produced for outcome measures that involve extensive procedure to derive analyzed outcomes.

Summary tables will display summary statistics calculated for each of the treatment groups, and overall. When the evolution of statistics over time is of interest, a group of rows that represent a cohort would generally be ordered chronologically.

The summary statistics displayed will be a function of the type of data associated with the summarized assessment. Continuous data will be summarized with the number of nonmissing values, mean, standard deviation (SD), minimum, median, and maximum. Categorical data will be summarized with the number of nonmissing values. Corresponding percentages will be calculated using the relevant analysis population set as the denominator, unless stated otherwise. Some continuous variables may also be grouped into categorical levels and evaluated in frequency tables.

PK concentrations and parameters will be summarized using n (for available data), mean, SD, coefficient of variation percent (CV%), median, minimum, and maximum values. Geometric means and geometric CV% will also be calculated for PK parameters.

All PK concentrations will be reported and analyzed with the same precision as the source data provided by the bio-analytical laboratory regardless of how many significant figures or decimals the data carry.

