Extra measurements (such as unscheduled or repeat assessments) will be included in subject listings but not in summary tables.

Figures will be produced as specified in sections to follow.

VI. Subject Accountability

A. Analysis Populations

A summary table will present counts and percent of subjects in the study analysis populations of Enrolled, Safety, Efficacy, and PK Analysis sets by treatment group.

B. Disposition

All subjects who discontinue treatment or withdraw early from the study will be included in a listing. Disposition summaries will present number of subjects enrolled, number treated, and among those treated number who completed and discontinued treatment. Primary reason for discontinuation of treatment, including any of the following, will be summarized:

- Adverse event
- Physician/Sponsor decision
- Pregnancy
- Protocol defined disease progression
- Study terminated by sponsor
- Subject non-compliance/Protocol violation(s)
- Withdrawal of consent.

Counts and percentages of subjects who withdraw early from the study for any of the above reasons will also be calculated using all members of the relevant population in the relevant treatment group for the denominator.

C. Subject Characteristics

The following subject characteristics collected for the Enrolled Analysis Set will be presented in data listings and summarized by treatment regimen and overall:

Demography:

- Age: Age will be calculated as the number of years elapsed between birth date and the date of the screening visit, adjusted for whether the birthday has passed as of the day of the screening visit.
- Sex at birth
- Ethnicity
- Race

Medical History:

- Medical history: As noted on the Medical History eCRF, any significant medical conditions present prior to signing consent will be presented in a listing and summary table. Verbatim terms will be coded using the MedDRA version 21.1 and ordered by system organ class (SOC) and preferred term (PT). At each level of summation (SOC, PT), subjects reporting more than one medical condition will be counted only once.
- AML disease information: Disease characteristics of initial diagnosis of AML recorded on the eCRF, along with time since initial diagnosis (calculated as date of informed consent – date of initial diagnosis of AML/365.25), will be listed and summarized.

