All AEs (whether TEAEs or not) will be listed by treatment group and individual subject, and include start and end dates, if the event was serious, seriousness criteria, CTCAE grade, relationship to study drug, action taken with study drug, and any other action. All TEAEs, Serious TEAEs, TEAEs that lead to study drug being permanently discontinued, and TEAEs resulting in death will be listed separately.

All AEs (whether TEAEs or not) will be summarized by system organ class and preferred term for each treatment group.

An overall summary table for TEAEs, and TEAEs occurring 10% or higher in the study population by preferred term and CTCAE grade will be provided. All TEAEs, grade 3 or greater TEAEs, TEAEs related to study drug (i.e., relationship to study drug deemed by the principal investigator as “Definite”, “Probable”, or “Possible”), grade 3 or greater TEAEs related to study drug, serious TEAEs, TEAEs leading to study drug being permanently discontinued, and TEAEs resulting in death will each be summarized by system organ class and preferred term. At each level of summation of system organ class and preferred term, subjects reporting more than one AE will only be counted once.

E. Deaths

All deaths and the primary cause of death will be listed.

F. Clinical Laboratory Results

Clinical laboratory tests for safety will be performed according to the study schedule, samples analyzed at local laboratories, and data entered directly into the electronic data capture system by site users.

Results for hematology and chemistry panels will be presented in separate data listings along with a flag for normal, abnormal not clinically significant, or abnormal clinically significant values. Listings will also be provided for pregnancy test, flow cytometry, and chromosomal/mutation testing.

Beginning with the baseline results, summaries of actual values at each assessment time point, and change from baseline will be presented by dose level and overall for each hematology and chemistry parameter. Change from baseline will be calculated as the post-baseline measurement minus the baseline measurement. If either the baseline or post-baseline value is missing, the observation will not be included in the change from baseline summary.

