A summary table will be constructed to display the anatomical main class (1st level) of each coded medication and, within that, the pharmacological subgroup (3rd level). It will include counts and percentages of subjects who reported using at least one medication in each pharmacological subgroup.

L. Blood Transfusions

Any blood transfusions received up to eight weeks prior to Cycle 1 Day 1 (baseline event), and during the study, including start and end dates, blood product, total number of units received, and reason for transfusion will be listed and summarized.

VIII. Efficacy Analyses

The secondary objectives of the study will be addressed using the Efficacy Analysis Set of subjects.

A. Disease Response

As per criteria defined in the ELN Guidelines by [Dohner et al, 2017](#), disease response will be assessed at screening and post-screening visits and included in a data listing. Additionally, anti-leukemic activity will be evaluated as per the following outcomes:

Response Rates: The distribution of best overall response (BOR) of CR, CRi, CRh, MLFS, or PR will be summarized by treatment cohort and overall. Point estimates with two-sided exact 95% and 90% confidence intervals (CIs) will be included for:

- Overall response rate (ORR) defined as the proportion of subjects who achieve a best overall response of CR, CRi, CRh, MLFS, or PR.
- Complete remission rate defined as the proportion of subjects who achieve a best overall response of CR.
- Complete remission with incomplete hematologic recovery rate defined as the proportion of subjects who achieve a best overall response of CRi.
- Complete remission with partial hematological recovery rate defined as the proportion subjects who achieve a best overall response of CRh.
- Morphological leukemia-free state rate defined as the proportion of subjects who achieve a best overall response of MLFS.
- Partial remission rate defined as the proportion of subjects who achieve best overall response of PR.

Additional information on precise definitions of these response categories can be found in Section 10.3 of the protocol.

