Duration of Response: Duration of response will be defined as the time from the first occurrence of a qualifying response of CR, CRi, CRh, MLFS, or PR, to the date when progressive disease is objectively documented or death due to any cause, whichever occurs earlier. Following the qualifying response, subjects who are alive without disease progression will be right-censored at the date of last disease evaluation. A Kaplan-Meier graph will be plotted by treatment group and estimates of median duration with associated 95% CIs will be reported.

Event-free Survival (EFS): Event-free survival will be determined from the first dose of brequinar to the date of relapse ($\geq 5\%$ bone marrow blasts, reappearance of blasts in blood, or development of extramedullary disease), disease progression, or death, whichever occurs first. Subjects who do not experience any of the three events will be right-censored at the latter date of disease evaluation or bone marrow sampling. A Kaplan-Meier graph will be plotted for time to the composite outcome by treatment group, and the estimate of medial survival time with 95% CI will be summarized.

Overall Survival (OS): Overall survival will be calculated as the time from the first dose of study drug to the date of death or right-censoring at the date of last subject contact. Median time to OS, with 95% CI, will be summarized and displayed graphically by treatment group using the Kaplan-Meier method.

B. Clinical Benefit

In addition to ORR, this study will examine clinical benefit to subjects. By treatment group, a summary table will report counts and percent of transfusion-dependent subjects at baseline who, in the absence of progression, CR or PR, and independent of marrow response, achieve one of the following:

- Erythroid response: Transfusion Independence (TI) for 8 or more weeks for subjects requiring at least 4 units of packed red blood cell transfusions in the previous 8 weeks. Only red blood cell transfusions given based on physician's judgment for a pretreatment hemoglobin (Hgb) of ≤ 8.5 g/dL will count in the red blood cell TI response evaluation.
- Platelet response: TI for subjects requiring a minimum of 4 platelet transfusions in the previous 8 weeks.

IX. Pharmacokinetic Analyses

The plasma PK of brequinar and DHO will be characterized using non-compartmental analysis. Where possible, the following standard PK parameters will be calculated:

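### OS, EFS and ORR are analysed only in subjects with a post-baseline response assessment, so treated subjects who die before one are lost from the survival curves and all unassessed subjects from the ORR denominator

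*SAP*

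**What the plan says.** SAP section V.E defines the Efficacy Analysis Set as those members of the Safety population having "measurable AML disease at baseline and at least one post-baseline disease response assessment. Subjects in this set will be used for all efficacy summary tables". Section VIII repeats the assignment: "The secondary objectives of the study will be addressed using the Efficacy Analysis Set of subjects". Section II.B lists ORR, OS, EFS and duration of response among those objectives.

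Section VIII.A starts both survival endpoints at first dose:

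- OS: "Overall survival will be calculated as the time from the first dose of study drug to the date of death", with censoring at last contact.
- EFS: "Event-free survival will be determined from the first dose of brequinar to the date of relapse", progression or death, whichever comes first. For the others: "Subjects who do not experience any of the three events will be right-censored at the latter date of disease evaluation or bone marrow sampling".

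Section V.F makes the relevant analysis set the denominator for percentages, and section V.D rules out imputation unless stated otherwise. No rule treats early death as an assessment or a missing assessment as non-response. No analysis of OS, EFS or ORR in all treated subjects is planned.

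**The concern.** Entry to the set depends on something that happens after the clock has started. A subject who is dosed and dies before the first response assessment has a known time origin, a known event and a known date, and no assessment is needed to observe any of them. The plan nevertheless removes that subject from the OS and EFS curves. Everyone who remains has, by construction, survived to an assessment, so the early part of each curve contains guaranteed survival (immortal time). Subjects who leave alive and unassessed are removed too, although their follow-up to last contact would count as censored OS time.

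For ORR and the CR, CRi, CRh, MLFS and PR rates, unassessed subjects drop out of the denominator. ORR is inflated whenever there is at least one responder and one such exclusion.

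Section IV.B enrols relapsed/refractory AML with available therapy exhausted, so deaths before a first assessment are plausible. The medians and curves would be labelled as running from first dose but would describe only those who reached an assessment.

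**Working it through.** **The plan's own figures.** The SAP gives no survival assumption, response target, early-death rate or assessment timing, and states that no formal sample size calculation applies. Only the headcount can be checked. Section IV.A gives 6 + 6 + 15 = 27 as planned and 5 + 6 + 15 = 26 after Cohort 1 stopped at 5, which is consistent with up to 27. I use 26.

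**Model (assumed).** Survival is exponential with true median *m*, the first assessment is at time *t0* for everyone, and death is the only reason for having no assessment. Then:

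- Excluded share = 1 − 2^(−t0/m).
- OS in the retained subjects is S(t)/S(t0), which reaches one half at t = m + t0. The apparent median is therefore m + t0.
- ORR is multiplied by 1/(1 − excluded share), because the responders are unchanged and only the denominator shrinks.

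Example with m = 3 months and t0 = 28 days (30.4375 days per month, so t0 = 0.92 months): excluded share = 1 − 2^(−0.92/3) = 19.1%, apparent median = 3 + 0.92 = 3.92 months, ORR factor = 1/0.809 = 1.24.

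| True median OS (months) | First assessment (days) | Excluded | Of 26 | Apparent median (months) | Change | ORR factor |
|---|---|---|---|---|---|---|
| 3 | 7 | 5.2% | 1.3 | 3.23 | +8% | 1.05 |
| 3 | 14 | 10.1% | 2.6 | 3.46 | +15% | 1.11 |
| 3 | 28 | 19.1% | 5.0 | 3.92 | +31% | 1.24 |
| 3 | 42 | 27.3% | 7.1 | 4.38 | +46% | 1.38 |
| 6 | 7 | 2.6% | 0.7 | 6.23 | +4% | 1.03 |
| 6 | 14 | 5.2% | 1.3 | 6.46 | +8% | 1.05 |
| 6 | 28 | 10.1% | 2.6 | 6.92 | +15% | 1.11 |
| 6 | 42 | 14.7% | 3.8 | 7.38 | +23% | 1.17 |

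**Kaplan-Meier illustration.** Take 26 death times placed at the quantiles of an exponential distribution with a 3-month median. The Kaplan-Meier median is 2.84 months in all 26. It becomes 3.53, 3.92 or 4.36 months after the 3, 5 or 8 earliest deaths are dropped.

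**EFS.** The effect on the median depends on the progression rate. At any time after t0, however, anyone still event-free was alive at t0 and is in the set, so the EFS probability is multiplied by 1/(1 − excluded share). With a 3-month median OS this is 1.05, 1.11, 1.24 and 1.38 for the four assessment times. A simulation of 1,000,000 subjects, with median time to progression of 2 or 4 months and progression documented only at assessments, gave the same four ratios for 3-month EFS under both progression rates.

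**ORR with the SAP's exact intervals (assumed 4 responders of 26 treated).**

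| Unassessed and dropped | ORR | Exact 95% CI |
|---|---|---|
| 0 | 4/26 = 15.4% | 4.4 to 34.9% |
| 3 | 4/23 = 17.4% | 5.0 to 38.8% |
| 6 | 4/20 = 20.0% | 5.7 to 43.7% |

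Results are also shown by cohort. If a cohort has a responder, one exclusion multiplies its ORR by 5/4 = 1.25 in Cohort 1 and by 6/5 = 1.20 in a Cohort 2 of 6.

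**The case against.** The strongest reply concerns size. The SAP does not say when the first response assessment falls, or whether an early visit without marrow sampling would count. With a 6-month median and an assessment at one week, fewer than one subject of 26 is lost and median OS moves by about 4%. If everyone is assessed, the condition has no effect. This stands: the larger figures are illustrations and should not set the severity.

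Second, a response-evaluable denominator is common in small early-phase studies, the analyses are descriptive, and the ORR shift is small against the interval width. This also stands, and makes ORR the lesser part. It does not help OS and EFS, which need no response assessment, and here the evaluable set is the only one rather than a supportive one.

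Third, the exclusions would be visible. Section VI.A tabulates "counts and percent of subjects in the study analysis populations of Enrolled, Safety, Efficacy, and PK Analysis sets by treatment group", section VII.E says "All deaths and the primary cause of death will be listed", and section V.F promises listings of recorded data, so a reader could identify the missing deaths. None of this supplies an OS or EFS estimate for all treated subjects.

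Fourth, moving ORR to the whole Safety Analysis Set also drops the measurable-disease condition, and a subject without measurable disease may be unable to show a response. The point is slight in a population enrolled with relapsed/refractory AML, and the present set would be kept as a supportive response analysis.

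**Conclusion.** The concern holds. Followed as written, the SAP removes observed early deaths from OS and EFS and removes all unassessed subjects from the response denominators; nothing in the document restores them. Deaths after a first assessment are unaffected.

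ORR inflation is certain given at least one responder and one unassessed subject. For OS and EFS an upward bias is the expected direction but is not guaranteed, because a subject who leaves unassessed and lives long could partly offset it.

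The size is unknown. It ranges from negligible to material over the assumed medians (3 and 6 months) and first-assessment times (1 to 6 weeks), and rests on exponential survival with death as the only cause of a missing assessment. The endpoints are secondary with no decision rule, so no test error rate is at stake. This should be fixed, mainly for OS and EFS.

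**What to change.** In sections V.E and VIII:

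- Analyse OS and EFS in the existing Safety Analysis Set (all subjects with at least one dose). The measurable-disease condition is fixed before dosing and does not cause this bias, but it is not needed to observe survival.
- Add to the EFS rule in section VIII.A that living subjects with no post-baseline disease evaluation are censored at first dose (Day 1), because the present rule gives them no post-dose date.
- Report ORR and its component rates in the same set, with unassessed subjects counted as non-responders.
- Keep the present set as a supportive analysis of response rates only, labelled response-evaluable. Duration of response stays in responders.

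The cost is SAP wording: one change of analysis set and one censoring sentence. If the protocol defines the same efficacy set, section XI also needs an entry. No new data are needed, since subjects who leave alive are censored at last contact for OS under the existing rule. Reported estimates would be expected to become slightly to moderately less favourable, depending on how many subjects have no assessment.

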Statistical code and outputs for analyses will be generated using SAS/STAT and SAS/GRAFH software, version 9.3 or higher, of the SAS system for Windows. Copyright © [2011] SAS Institute Inc. SAS and all other SAS Institute Inc. product or service names are registered trademarks or trademarks of SAS Institute Inc., Cary, NC, USA.

A. Data Sources

The study center staff will record completion and results of required study procedures in an electronic case report form (eCRF). The following external data obtained from third-party vendors for this study will be combined with eCRF data for analysis:

Vendor Name	Contact Information	Data Type	Schedule	Reconciliation Items
Pyxant	TBD	DHO plasma levels and brequinar PK results	2 transfers during study	Header data (subject ID, initials, visit, lab date, lab time)

B. Multiple Study Centers

Data analyses will be pooled and not controlled for center effect.

C. Definition of Baseline

Baseline will be defined as the last measurement collected before the first dose of study drug. As such, height and body surface area assessed at Screening, and pre-dose assessments made on Cycle 1 Week 1 Day 1 for weight, vital signs, hematology/chemistry, and 12-lead ECG will serve as valid baseline measures. A missing value at Cycle 1 Week 1 Day 1 will default to the Screening measurement.

For this study, since there is no day 0, the day immediately prior to study day 1 will be Day -1 [calculated as Event Date – Date of First Treatment]. For events on or after first dose of study drug, study day will be calculated as [Event Date – Date of First Treatment + 1]. Thus, first day of study drug dose will be Day 1.

D. Missing Data

Unless stated otherwise in sections below, missing data will not be replaced with imputed values.

E. Analysis Populations

Four analysis population sets will be defined for use with various analyses, namely:

- The Enrolled Analysis Set will include all subjects who sign informed consent, meet the inclusion/exclusion criteria and are enrolled in the study. Demographics and disposition summaries will be reported for this set of subjects.
- The Safety Analysis Set will include all subjects who are enrolled in the study and receive at least one dose of brequinar. Subjects in this set will be used for all safety/tolerability summary tables.

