Summary statistics will be presented for assigned dose level, cumulative assigned dose, cumulative actual exposure (mg), total duration of treatment (calculated as the number of weeks from date of first drug dose to date of last drug dose), dose intensity (calculated as cumulative actual exposure divided by treatment duration, mg/week), relative dose intensity (calculated as a percent of cumulative actual drug dose divided by cumulative assigned dose), and any reason for missed dose.

B. DHO Plasma Levels

In addition to safety/tolerability, intra-subject dosing for this study will be guided by DHO levels measured using a validated assay. A subject listing will include baseline and trough DHO levels (ng/ml), as well as the following additional characteristics noted at each scheduled visit:

- Previous assigned dose (mg/m²).
- DHO dose adjustment (dose not changed, escalated by 150 mg/m², held, Cohort 1 dose escalation not permitted).
- Assigned dose based on DHO (mg/m²).
- PI evaluation of whether subject has acceptable safety, safety dose adjustment, and assigned dose.
- Actual dose (mg).
- Agreement between PI assessment and actual dose (No/Yes, reason for disagreement).

The above dose-modification characteristics will also be summarized by treatment group and overall.

C. Dose Limiting Toxicities

AEs identified as protocol-defined DLTs will be listed and will include start and end dates, CTCAE grade, relationship to study drug, outcome, and action taken. Number and percentage of subjects reporting DLTs in each treatment group, and overall, will be summarized.

D. Adverse Events

AEs will be collected from time of informed consent through at least 14 days after the final dose of study medication. Any pre-existing condition that changes in severity after dosing or abnormal laboratory finding will be recorded as an AE. Events that occur prior to dosing will be recorded as medical history. A TEAE for this study will be defined as an AE occurring after the first dose of the study treatment through 30 days after the last dose of study treatment.

Verbatim terms on the eCRF will be coded using the MedDRA version 21.1 and displayed hierarchically by system organ class and preferred term. Multiple incidences of the same AE for a subject will be counted only once at the maximum CTCAE grade.

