For hematology parameters leukocytes, hemoglobin, and platelets that can be graded using the NCI CTCAE criteria, shift tables that summarize counts and percentages of subjects by severity grade at baseline and worst post-baseline result will also be constructed.

The percentage of blasts in bone marrow ascertained via aspiration and biopsy will be listed and summarized.

G. Vital Signs

At designated visits, vital signs will be recorded and will include weight, temperature, heart rate, respiratory rate, and systolic and diastolic blood pressure. A listing of all vital signs, along with height and derived body surface area, will be provided. Additionally, data will be summarized by dose group and overall, using descriptive statistics at baseline, each study evaluation, and change from baseline to evaluation. Change from baseline will be calculated as the post-baseline measurement minus the baseline measurement. If either value is missing, the observation will not be included in the change from baseline summary.

H. 12-Lead Electrocardiogram

12-lead ECG data, obtained at scheduled visits, will be listed. Counts and percentages of subjects with normal, abnormal clinically significant, and abnormal not clinically significant evaluations will be summarized at each time point.

I. ECOG Performance Status

ECOG performance status assessed at Screening will be listed and summarized for each numeric grade.

J. Physical Examination

Confirmation of a physical examination, including date of assessment, will be listed for each scheduled time point.

K. Concomitant Medications

Any medication or treatment taken within two weeks prior to study entry as well as during the course of the study will be recorded in the eCRF. Indication for use, start date (if known), dose frequency, route, and whether ongoing or stopped will also be noted.

Verbatim terms from the eCRF will be mapped to Anatomical/Therapeutic Chemical class and Generic drug names using the WHODD version September 2018 Enhanced B2.

For each dose cohort, a listing will display all entries for medications received by a subject, ordered by “Start date”. The listing will display the recorded term from the eCRF and, adjacent to that, the WHO Drug pharmacological subgroup and the anatomical main class that appears in the tables.

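### The rule keeping unscheduled and repeat assessments out of all summary tables turns the worst post-baseline grade in the hematology shift tables into the worst scheduled grade

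*SAP*

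**What the plan says.** Five parts of the SAP bear on this.

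- **Section V.F, extra measurements.** "Extra measurements (such as unscheduled or repeat assessments) will be included in subject listings but not in summary tables". No qualifying clause is attached.
- **Section V.F, displays.** Only three kinds of display are planned: listings, summary tables and figures. Summary tables are shown for each treatment group and overall. On denominators: "Corresponding percentages will be calculated using the relevant analysis population set as the denominator, unless stated otherwise".
- **Section VII.F (Clinical Laboratory Results).** For leukocytes, hemoglobin and platelets the plan calls for "shift tables that summarize counts and percentages of subjects by severity grade at baseline and worst post-baseline result". It does not limit the worst result to scheduled visits and does not exempt these tables from the V.F rule. The same section plans, for every hematology and chemistry parameter, "summaries of actual values at each assessment time point, and change from baseline will be presented by dose level and overall".
- **Section V.C (Definition of Baseline).** "Baseline will be defined as the last measurement collected before the first dose of study drug". For hematology, the pre-dose assessment on the first dosing day serves as baseline, and "A missing value at Cycle 1 Week 1 Day 1 will default to the Screening measurement".
- **Section VII.D (Adverse Events).** "Any pre-existing condition that changes in severity after dosing or abnormal laboratory finding will be recorded as an AE", and "Multiple incidences of the same AE for a subject will be counted only once at the maximum CTCAE grade".

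**The concern.** Leaving extra draws out is sensible for summaries by time point, where an unscheduled value has no visit to belong to. It does not suit a worst-value statistic, which is meant to cover the whole post-baseline period. A subject whose lowest count falls on an unscheduled draw would be placed in too low a grade, while a reader takes the table to show the worst of all results.

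Safety and tolerability is the primary objective, and these tables are part of how it is reported. An abnormal laboratory finding is also recorded as an adverse event and counted at its maximum grade. The adverse event table and the shift table could therefore show different worst grades for the same subject, with nothing in the report to explain why.

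**Working it through.** The SAP gives no figure to reproduce here. The check has four parts: whether the rule reaches the shift tables, the direction of the error, the baseline, and the weight of one subject.

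**1. Does the rule reach the shift tables?** V.F allows listings, summary tables and figures. A shift table gives counts and percentages of subjects, so it is a summary table. Where the SAP wants a default that other text may override, it says so, as for missing data (V.D) and for listings and percentages (V.F). The sentence on extra measurements carries no such clause. As written, it applies.

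**2. Direction for the worst grade.** Let S be a subject's scheduled post-baseline results and A all recorded post-baseline results, with S contained in A. The worst grade is a maximum, so max(S) ≤ max(A). A hypothetical case: scheduled grades 2 and 3 and one unscheduled grade 4 give max(2, 3) = 3 under the rule and max(2, 3, 4) = 4 over all results.

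An enumeration of grades 0 to 4, with 1 to 3 scheduled and 0 to 2 extra values, covers (5 + 25 + 125) × (1 + 5 + 25) = 155 × 31 = 4805 patterns. The scheduled-only worst grade is lower in 1248, equal in 3557 and higher in 0. These are counts of patterns, not probabilities.

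**3. Direction for the shift from baseline.** V.C settles most baselines: the first dosing day, else Screening. The exception is an unscheduled or repeat pre-dose sample that is the last value before first dose. It meets the V.C definition, but V.F keeps it out of the table. Take one scheduled and one such extra baseline value, and one scheduled and one extra post-baseline value, each graded 0 to 4. Of the 5⁴ = 625 patterns, the scheduled-only shift is larger than the full-data shift in 185, smaller in 335 and equal in 105. The shift can therefore move either way.

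**4. Weight of one affected subject.** For each parameter, the correct grade loses one subject and a lower grade gains one, so each of the two cells changes by 1/n. The sizes come from section IV.A: up to 27 subjects; 5 enrolled in Cohort 1, about 6 in Cohort 2 and about 15 in the expansion cohort. All are assumed to be dosed.

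| Group | n | 1/n |
|---|---|---|
| Overall, stated maximum | 27 | 3.7 points |
| Overall, 5 + 6 + 15 | 26 | 3.8 points |
| Cohort 1 | 5 | 20.0 points |
| Cohort 2 | 6 | 16.7 points |
| Expansion | 15 | 6.7 points |

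The cohort rows are the planned display only if treatment group means cohort.

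**How many subjects?** The SAP does not allow an estimate. Purely as an assumption, let a share q of 27 subjects have their worst grade only on an extra draw. The expected number misplaced is 27q, and the chance of at least one is 1 − (1 − q)²⁷:

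- q = 5%: 1.35 expected, chance 0.75
- q = 10%: 2.7 expected, chance 0.94
- q = 20%: 5.4 expected, chance 0.998

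The true q may be zero.

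**The case against.** The strongest reply is that the conflict disappears if the specific text governs the general. V.F is a general rule on display, while VII.F asks for the worst result without limiting it to scheduled visits. A sensible programmer might follow VII.F. That reading is possible, but the SAP does not state it, and the unqualified sentence in V.F points the other way. Two programmers could each follow the document and produce different tables.

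A second reply concerns direction. If a repeat was drawn because the scheduled sample was invalid, barring the repeat can overstate the true grade. With two scheduled values, one of them replaced by a repeat, the 125 patterns divide into 30 over, 30 under and 65 equal. The SAP has no replacement rule, so this does not remove the point, but it does confine the one-way direction to valid results. A reader might infer that the tables can only ever flatter the drug. The documents do not support that for invalid samples or for the shift from baseline.

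A third reply is that little depends on these tables, and this stands. All safety analyses are descriptive (section V). Unacceptable toxicity is defined through adverse events (III.A), and dose-limiting toxicities and treatment-emergent events have their own tables (VII.C, VII.D). Every value stays in the listings with a clinical-significance flag. The percentages in the working show only what one subject weighs in a table of that size; they are not evidence that anyone is misplaced.

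Finally, a mismatch between the adverse event and shift tables would not prove that this rule caused it. The treatment-emergent window closes 30 days after the last dose, whereas the shift tables are simply post-baseline.

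**Conclusion.** The point holds for the three hematology shift tables. As written, V.F makes them report the worst scheduled result under a label that promises the worst result. Relative to all recorded valid results, the worst post-baseline grade can be understated but not overstated. The shift from baseline may move either way in the uncommon case where an extra pre-dose value is the last before first dose.

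Each affected subject moves two cells per parameter by about 3.7 points overall and, if treatment group means cohort, by 20.0, 16.7 or 6.7 points. This rests on all enrolled subjects being dosed and on the planned cohort sizes being reached. The number affected is unknown and may be zero.

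A reader might infer that the trial's safety conclusions are biased. The SAP does not support that: no estimate, test or decision rule uses these tables, and the listings and adverse event tables partly make up for them. Those safeguards do not correct the shift tables themselves, so the wording is worth changing.

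**What to change.** Keep the V.F exclusion for summaries by time point, and add to sections V.F and VII.F:

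> For the hematology shift tables, the worst post-baseline CTCAE grade will be derived from all valid post-baseline results, including unscheduled and repeat assessments, and baseline will be the last valid value before first dose, whether scheduled or not; a result documented as invalid and replaced by a repeat will not be used.

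The wording is deliberately limited to the shift tables. A broader rule admitting extra values to every summary not organised by visit would also change tables such as the bone marrow blast summary, for which VII.F names no time points.

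The cost is a one-sentence SAP change and slightly more programming; the data are already collected and listed. Worst-grade counts may look slightly less favourable than under the present rule.
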